#### At the Time of Stent Removal

The participants will be asked to complete the following questionnaires prior to stent removal:

- Ureteric Stent Symptoms Questionnaire 1 with Analog Pain Scale included (USSQ 1 stent in situ)
- AUA Symptom Score Questionnaire
- Satisfaction Questionnaire

In addition, the patients will be asked to share with us the number of days pain pills have been taken, and their compliance with tamsulosin and docusate. We will assess for any use of anticholinergics, other analgesics and antibiotics.

The participants will then undergo cystoscopic removal of the stent in clinic.

Results of any standard of care imaging obtained prior to stent removal will be collected.

## Day 7 Post-Stent Removal

On day 7 post stent removal, participants will be asked to complete:

- Ureteric Stent Symptoms Questionnaire 2 with Analog Pain Scale included (USSQ 2 post stent)
- AUA Symptom Score Questionnaire
- Satisfaction Questionnaire

Copies of the surveys along with addressed and stamped envelopes will be given to the participants at the time of office visit for stent removal. Surveys will be self-administered at home and mailed back to the research center. Reminder phone calls will be made to the participants to assure compliance.

## ***Outcome measures***

1. Stent
  - a. Type
  - b. Composition (soft or hydrophobic)
  - c. Length
2. Stent complications
  - a. Migration
  - b. Malposition
  - c. Dislodgement
  - d. Need for re-insertion
3. Time to stent removal
  - a. Clinically planned or required due to symptoms
4. Health Related Quality of Life
  - a. Ureteric Stent symptoms Questionnaire 1 and 2
  - b. AUA Symptom
5. Pain Score as reported by the participants on the self-administered assessment
6. Procedure Satisfaction Questionnaire
7. Use of analgesics for pain control
  - a. documented pain prescription at the time of discharge
  - b. self-reported duration of analgesics use after stent insertion (in days)
8. Residual stone burden
  - a. KUB, U/S, CT

## ***Covariate data***

1. Gender
2. Race

3. Height
4. Weight
5. Patient medical/surgical history
6. Type of procedure
7. Etiology of disease

### ***Sample size calculation and statistical analysis***

[figure not shown]
#### **Power Analyses**

Power is the probability to detect statistically significant results from a sample, if one actually exists in the population. In order to determine the sample size needed for adequate power, we are using an alpha (criterion of significance) of 0.05 in a two-tailed (non-directional) test (Figure) as our primary outcome is the pain index score.

Since there isn't a pilot study or previous work to base the assumptions of the power analysis, 216,000 simulations were performed varying sample size ( $n=100,150,200$ ), standard deviation of the population ( $\sigma=1,3,5$ ), and assumed true difference in population means of the pain index score (24 differences ranging from 0.1 to 4.7). For each combination of sample size, population standard deviation, and difference in population mean, 1000 simulations were tested. The results for these simulations are displayed graphically in Figure 1. The power analysis was calculated for soft versus hydrophobic stents.

Because of the uncertainty of the assumptions of the power analysis, it is recommended to perform an interim analysis at  $N=100$ . If there is low variability in the populations or if the true difference of the population is greater than 3 (or some combination of the two), 100 samples would potentially provide ample power to detect the differences in the populations.

Figure 1.

### Planned Statistical Analysis

We will evaluate parameters, including stent composition, and outcomes including complications, hematuria, pain medication requirements, return to work/normal activities, subjective assessments of pain, discomfort and satisfaction, and factors associated with stent removal, including periprocedural discomfort, and need for early/delayed removal of the stent. We will use t-test, U-test, ANOVA, chi-squared tests, and multivariate statistical methods to evaluate our outcomes.

After 100 patients are accrued, an interim analysis will be performed in order to determine if the research questions are statistically significant at the 0.05 level. If they are significant results, patient enrollment will end. If they are not significant, a second power analysis will be performed to determine if 100 more patients would provide reliable statistical power of achieving significant results. This power analysis will be much more informative as there would be actual estimates of the populations of interest. If it is determined that an additional 100 more patients would still be unlikely to yield statistically significant results, patient enrollment will end. If it is determined that an additional 100 patients would be likely to yield statistically significant results, an additional 100 patients will be enrolled into the study.

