## INTRODUCTION

Ureteral stents are commonly-employed during routine stone procedures, including ureteroscopy, percutaneous nephrolithotomy, and shockwave lithotripsy. Their primary function is to preserve drainage and decompression of urine on the affected side. After stone procedures, they are commonly employed to counteract ureteral swelling which may otherwise temporarily impair drainage.

Though considered a staple of modern urology, ureteral stents are nonetheless the source of complaints from patients, who often report significant bother associated with the presence of a stent. Symptoms include urinary urgency and frequency from irritation of the bladder by the stent, pain in the back associated with reflux of urine along the stent, minor aches and cramping from the stent itself, blood in the urine, and discomfort during removal in the office. Over the past few decades, newer and smaller stents have become available; however, studies evaluating the impact of these newer stent technologies have been conflicting. Catheter/stent diameter is measured in French scale (Fr.). The french size is a measurement of external diameter of the catheter, not the internal drainage channel. (Fr. = D (mm) x 3) We plan to use 6Fr soft and hydrophobic, to prospectively evaluate the effect of stent composition upon patient comfort and satisfaction following stone surgery.

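### Discomfort at stent removal is a planned, non-primary outcome, but no patient-reported measure is specified for when it occurs: the removal-visit forms come before removal and the next are due about a week later.

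*Combined protocol and SAP*

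**What the plan says.** The Introduction includes "discomfort during removal in the office" in its list of stent symptoms. The Planned Statistical Analysis section then lists, among the things to be evaluated, "factors associated with stent removal, including periprocedural discomfort", followed by the need for early or delayed removal.

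The section At the Time of Stent Removal fixes the order of events at that visit. Of the three forms (USSQ 1 with analog pain scale, AUA Symptom Score, Satisfaction Questionnaire) it says: "The participants will be asked to complete the following questionnaires prior to stent removal". Patients are also asked about "the number of days pain pills have been taken, and their compliance with tamsulosin and docusate", and about use of anticholinergics, other analgesics and antibiotics. Only after this does removal follow: "The participants will then undergo cystoscopic removal of the stent in clinic".

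The next report is introduced by "On day 7 post stent removal, participants will be asked to complete". That set is USSQ 2 with analog pain scale, the AUA Symptom Score and the Satisfaction Questionnaire. The forms are handed over at the removal visit with stamped envelopes, filled in at home and mailed back, and reminder calls are made. Table 1 gives this time point a window of ± 1 day.

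**The concern.** A patient cannot rate the discomfort of a procedure that has not yet happened. If every form at the removal visit precedes removal and the next is due a week later, an outcome named in the analysis section has no specified source of data from the time it occurs.

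The topic is relevant to the trial, whose research question is whether one stent is more comfortable than the other. Discomfort at removal is brief and is best rated on the spot; an immediate rating cannot be recovered later. Without one, the comparison may go unreported, or it may be assembled afterwards from Day 7 answers that were not specified for the purpose. Such answers would follow a week of post-stent symptoms and would be missing for anyone who does not return the forms.

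**Working it through.** The plan gives no figure for this outcome, so there is none to reproduce. The check is to set the schedule beside the planned outcome.

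**Step 1. List every scheduled patient-reported form, from the visit sections and Table 1.**

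- Screening/baseline: AUA Symptom Score and analog pain scale (2 forms).
- Day 0, stent insertion: none.
- Removal visit, before removal: USSQ 1 with pain scale, AUA Symptom Score, Satisfaction Questionnaire (3 forms).
- Removal visit, during or after removal: none.
- Day 7 (± 1) after removal: USSQ 2 with pain scale, AUA Symptom Score, Satisfaction Questionnaire (3 forms).

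The total is 2 + 3 + 3 = 8 form completions per patient. None falls at removal or between removal and the Day 7 window. The separate analog pain scale row of Table 1 is marked at screening only.

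**Step 2. Interval from removal to the next report.** With the Table 1 window, the earliest is 7 − 1 = 6 days and the latest is 7 + 1 = 8 days.

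**Step 3. Other sources at the removal visit.**

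- The additional questions put to the patient concern medication use, and they too are described ahead of removal.
- Table 1 marks Procedure Data Collection at removal. Its content is not defined.
- Table 1 marks Adverse Events at removal. Nothing says that this includes a patient rating of discomfort.
- Imaging data at removal are not a patient report.

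**Step 4. Outcome list.** The Outcome measures section has a general self-reported pain score, a procedure satisfaction questionnaire and the two USSQ forms. It has no entry for discomfort at removal.

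**Step 5. Day 7 content.** The items of USSQ 2 and of the Satisfaction Questionnaire are not in the documents. If one of them asks about the removal, the answer is a recall over 6 to 8 days. If neither does, the outcome is not measured by any specified form.

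**Step 6. Reach.** The Power Analyses section names the pain index score as the primary outcome and bases the simulations on it. Discomfort at removal enters neither the sample size nor the power figures.

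**The case against.** The strongest reply is that the documents do not show the data to be absent. Procedure Data Collection is marked at removal, and the case report form behind it could hold a discomfort item. The satisfaction form, which the Outcome measures section ties to the procedure, is repeated after removal and may ask about it. This part stands. A reader might infer that the comparison cannot be answered at all from data collected at the time; the documents do not support that, because the content of these sources is unknown. What they support is that no measure is specified. If such an item does exist, the plan still needs to name it.

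A second reply is that the outcome is minor. This also stands in part. A reader might infer that the protocol treats discomfort at removal as a main stent complaint, but the Introduction lists it among several symptoms without ranking them. It appears once in the analysis section, within a broad list, and is not primary.

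A third reply is that recall does no comparative harm, since both arms follow the same schedule and patients are blinded. A reader might infer bias between the stents, but nothing in the documents shows any; the expected effect is noise. Stamped envelopes and reminder calls also reduce the loss of forms. They do not shorten the recall.

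A fourth reply is that periprocedural discomfort could be read to include discomfort before removal, or symptoms that prompt early removal. USSQ 1 and the recorded reason for removal would cover part of that. The reading is possible, but less natural: the wording ties the discomfort to removal, early or delayed removal is listed as a separate item, and the Introduction speaks of discomfort during removal.

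**Conclusion.** The point holds as a mismatch between a planned outcome and the measurement schedule. None of the 8 scheduled form completions falls at or just after removal, and the first possible later report is due 6 to 8 days on. As specified, discomfort at removal is either unmeasured or recalled after about a week, with added noise and dependence on the return of mailed forms.

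Its size is moderate. It affects one non-primary comparison and leaves the primary outcome and the sample size untouched. It goes beyond a missing detail, because following the schedule exactly yields no contemporaneous patient rating from any named instrument.

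The conclusion rests on two assumptions: that the phrase in the analysis section means discomfort caused by the removal itself, and that the undefined data collection at removal holds no patient rating. If the second is wrong, the remaining defect is that the plan does not name its measure.

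**What to change.** Add one analog pain rating immediately after cystoscopic removal, before the patient leaves clinic and without disclosing stent type. The documents do not say when patients are unblinded, so the instruction not to disclose should be written in.

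Four edits carry it:

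- At the Time of Stent Removal: add the rating after the removal step.
- Outcome measures: add an entry for discomfort at removal, distinct from the general pain score.
- Table 1: mark the rating in the Stent Removal column, labelled as post-removal so that it is not confused with the pain scale inside USSQ 1.
- Planned Statistical Analysis: name this rating as the measure of periprocedural discomfort.

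The cost is about one minute of patient time and one more data item, using a scale already in the study at a visit that already takes place. If the case report form or a Day 7 form already asks about removal, cite the item and its time point as well. If the sponsor does not want the measure, delete the outcome from the analysis section.

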#### **Baseline**

Once informed consent for study participation is obtained, patients will be asked to complete:

- AUA Symptom Score Questionnaire
- Analog pain scale

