#### Day 0 (Stent Insertion)

Randomization will take place prior to the procedure. Patients will be randomized in a 1:1 ratio for stent composition, soft vs. hydrophobic, for a total of 50 patients in each cohort. To minimize selection bias, a randomization table will be developed before initiation of enrollment. Envelopes containing randomization assignments will be created, sequentially numbered and sealed. Once enrollment is initiated, randomization envelopes will be opened for each subject after informed consent is granted and study eligibility is confirmed. Subjects will be blinded to the stent assignment so their reported pain level and satisfaction is not influenced by the knowledge of the inserted stent type.

The surgical procedure for stone management will be performed via an approach consistent with current standards-of-care.

Patients will be discharged on a standard regimen, consisting of Norco, or an equivalent narcotic, tamsulosin, and docusate. Patients will not be placed on anticholinergic or phenazopyridine medications at discharge.

When clinically indicated, exchange of stent is permitted. The patient data will be evaluable so long as adherence to initial randomization stratification is maintained.

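### No test is named for the pain comparison that can end enrolment at 100 patients, and the baseline pain score is collected but unused; one pre-specified ANCOVA would settle both

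*Combined protocol and SAP*

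**What the plan says.** The Power Analyses section states that "our primary outcome is the pain index score". It plans a two-tailed test at 0.05 and varies the "assumed true difference in population means of the pain index score". The comparison behind the sample size is therefore a difference in means between soft and hydrophobic stents.

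The Planned Statistical Analysis section assigns no method to that outcome. For all outcomes together it says: "We will use t-test, U-test, ANOVA, chi-squared tests, and multivariate statistical methods to evaluate our outcomes". Once 100 patients are accrued, "an interim analysis will be performed in order to determine if the research questions are statistically significant at the 0.05 level". A significant result ends enrolment. Otherwise a second power analysis decides whether to add 100 patients, and of this the plan says: "This power analysis will be much more informative as there would be actual estimates of the populations of interest".

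The Baseline section and Table 1 collect the "Analog pain scale" at screening, up to 28 days before surgery. The Covariate data section lists gender, race, height, weight, history, procedure type and etiology, but not baseline pain. Pain is measured again on an analog scale inside USSQ 1 (before stent removal) and USSQ 2 (day 7 after removal). No USSQ is given at baseline. The plan does not say which of these scores, or which time point, is the pain index score.

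**The concern.** There are two gaps. First, a p-value below 0.05 stops recruitment, but the test that yields it is not fixed. With two arms, ANOVA is the same test as the equal-variance t-test, and chi-squared does not suit a score. The real options are therefore the t-test, the U-test or some multivariate model. If the choice is made after the data are seen, the 5% level is no longer 5%, and two defensible tests can give opposite stopping decisions.

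Second, a pre-randomisation measure of pain is in hand, with no commitment to use it. If it predicts later pain, adjusting for it gives a tighter estimate without collecting anything more. It would also give a smaller residual SD for the second power analysis.

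**Working it through.** **Inputs from the documents.** Two-sided alpha 0.05; 50 per arm at the 100-patient look (Day 0 section); 100 per arm if extended; SD 1, 3 or 5; 24 differences from 0.1 to 4.7; 1000 runs per combination (Power Analyses).

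**Assumed.** The baseline–outcome correlation r is not given, so 0 to 0.5 is shown. It may be low, because baseline precedes surgery by up to 28 days and precedes the study stent. No dropout is applied.

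**1. The plan's own figures.** 3 sample sizes × 3 SDs × 24 differences × 1000 = 216,000, as stated. The plan says 100 patients would potentially be ample if the true difference exceeds 3. To check at difference 3, use SE = SD × √(2/50) = 0.2 × SD on 98 df (noncentral t):
- SD 5: SE 1.0, noncentrality 3/1.0 = 3.0, power 84.4%.
- SD 3: SE 0.6, noncentrality 3/0.6 = 5.0, power 99.9%.
- SD 1: power above 99.9%.

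This agrees with the plan's statement. Figure 1 is not available for comparison.

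**2. Adding baseline pain.** With n per arm and one covariate, SE = SD × √(1−r²) × √[(2/n) × (1 + 1/(2n−4))], on 2n−3 df. At n = 50 the inflation factor is 1 + 1/96 = 1.0104, on 97 df. For SD 5 and r = 0.3, SE = 5 × √0.91 × √(0.04 × 1.0104) = 0.959. The noncentrality is 3/0.959 = 3.13 and power is 87.2%.

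| Scenario | Unadjusted | r = 0 | r = 0.1 | r = 0.3 | r = 0.5 |
|---|---|---|---|---|---|
| 50 per arm, SD 5, difference 3 | 84.4% | 84.0% | 84.4% | 87.2% | 92.7% |
| 50 per arm, SD 3, difference 1.5 | 69.7% | 69.2% | 69.7% | 73.3% | 81.1% |
| 50 per arm, SD 3, difference 3 | 99.9% | 99.8% | 99.9% | 99.9% | >99.9% |
| 100 per arm, SD 5, difference 2 | 80.4% | 80.2% | 80.6% | 83.7% | 90.0% |

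The equivalent unadjusted sample for 100 adjusted patients is 100/[(1−r²) × 1.0104] = 99, 100, 109 and 132 for the four values of r. Break-even is at r of about 0.10 with 50 per arm.

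**3. An open choice of test, no true difference.** Simulation with normal data and 50 per arm (40,000 runs at each r):
- t-test alone, or ANCOVA alone: about 5%.
- Smaller p of t and U: about 6%.
- Smallest p of t, U and ANCOVA: about 6.2% at r = 0, 7.2% at r = 0.3 and 8.0% at r = 0.5. Other runs gave 6.8% to 7.8% for r of 0.3 to 0.5.

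With SD 5 and difference 3, the t-test and U-test disagree on significance in about 4.5% of simulated trials.

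**4. Cost against the U-test on a skewed score.** Assumed right-skewed 0–10 integer score, means 3.4 and 2.3, SDs about 2.7 and 2.1, 50 per arm, 6,000 runs per r:

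| r | U-test power | ANCOVA power |
|---|---|---|
| 0 | 64.7% | 59.6% |
| 0.1 | 65.8% | 60.4% |
| 0.3 | 64.2% | 62.7% |
| 0.5 | 64.1% | 68.8% |

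A separate run on a skewed 0–10 score gave a deficit of about 4 points at r = 0 and 1 point at r = 0.3, and a lead of 5 points at r = 0.5. On the score tabulated above, t and U disagreed in about 13–14% of trials.

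**The case against.** The case against is that the gain is speculative. An unadjusted comparison is valid, r is unknown and may be low, and at r = 0.1 nothing is gained. The Power Analyses section already points to a comparison of means, which suggests the t-test. The inflation from choosing among tests arises only if someone chooses after seeing results. The covariate list and the mention of multivariate methods show that adjustment was contemplated. On a skewed score, the U-test can beat ANCOVA.

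Much of this stands and limits the point. The power gain cannot be promised, and the loss of about 0.4 points at r = 0 (SD 5, difference 3) holds only against the t-test on normal data. But the framing of the power calculation is not carried into the analysis section, and permitting adjustment is not the same as committing to it. The case for naming one test does not depend on r, and it is stronger on skewed data, where the candidate tests disagree more often. ANCOVA is the reasonable test to name because it targets the difference in means on which the plan is powered.

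A reader might also infer that the analog scale must be made primary because only it has a baseline on the same instrument. The documents do not require this: baseline analog pain is a valid covariate for a USSQ pain score too. The choice of primary score belongs to the sponsor.

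**Conclusion.** The point holds as an inexpensive improvement in pre-specification and efficiency. The test behind the stopping decision is unnamed, and baseline pain is used in no stated analysis. Leaving the choice open can take the 5% level to about 6%, or to 7–8% with ANCOVA as a third option at r = 0.3 to 0.5. These are upper figures for someone who takes the smallest p-value; nothing in the documents shows an intention to do so. The power gain at 50 per arm, SD 5 and difference 3 runs from −0.4 points (r = 0) to +8.3 (r = 0.5), and is negligible at SD 3 and difference 3, where power is already about 99.9%.

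A reader might infer that the planned analysis is invalid without adjustment. It is not: randomisation makes the unadjusted test valid. Nor would ANCOVA repair the use of 0.05 both at 100 and again at 200 patients, which needs its own rule.

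**What to change.** Before the 100-patient data are examined:

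1. State which pain score, and at which time point, is the primary outcome. Express the SDs and differences in the Power Analyses section in that score's units.
2. Make the primary analysis, at 100 patients and at any final look, one ANCOVA on randomised arm and baseline analog pain. Report the adjusted mean difference with its 95% CI.
3. Keep the t-test and U-test as sensitivity analyses that do not drive stopping.
4. Replace skipped baseline scores by the overall mean, computed without regard to arm, since patients may skip questions (Risks and Benefits). With an assumed 10% missing at random, simulated level stayed at 0.049 to 0.052, and power was 83.9%, 87.0% and 91.8% at r = 0, 0.3 and 0.5 (SD 5, difference 3).
5. Use the ANCOVA residual SD in the second power analysis.

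If procedure type, which is on the covariate list, is added, use the planned procedure. The plan says "Randomization will take place prior to the procedure", so the procedure as performed is a post-randomisation variable.

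The cost is wording plus the decision on the primary score; no new data are needed. If baseline predicts nothing, about 0.4 points of power are lost against the t-test on normal data (SD 5, difference 3). About 4 to 5 points could be lost against the U-test if the score is strongly skewed.

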## METHODS

### *Study design*

This is a single institution, randomized, single-blinded study to evaluate patient comfort and satisfaction following surgical stone management procedure with randomization allocation ratio of 1:1 (size 6Fr, soft; size 6Fr, hydrophobic;). Catheter diameter is measured in French scale (Fr.) the french size is a measurement of external diameter of the catheter, not the internal drainage channel. (Fr. = D (mm) x 3)

This study will be conducted at Washington University and will enroll 100 participants.

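### The AUA Symptom Score is collected before the stent as well as after it, but the analysis plan does not say how the baseline score will be used, so a possible gain in precision is not secured.

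*Combined protocol and SAP*

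**What the plan says.** In the combined protocol and SAP, the Baseline section lists the "AUA Symptom Score Questionnaire" and an analog pain scale, both completed after consent. The AUA form is repeated before stent removal and on Day 7 after removal, and Table 1 confirms all three times. Outcome measures places AUA under health-related quality of life (item 4b).

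The methods are given in one sentence of Planned Statistical Analysis: "We will use t-test, U-test, ANOVA, chi-squared tests, and multivariate statistical methods to evaluate our outcomes". It does not say which method goes with which outcome. It also does not say whether AUA will be compared as a follow-up value, as a change from baseline or with adjustment for baseline. That section's list of outcomes does not name AUA.

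Covariate data has seven entries: gender, race, height, weight, "Patient medical/surgical history", procedure type and disease etiology. Neither baseline AUA nor baseline pain is among them.

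Power Analyses says "we are using an alpha (criterion of significance) of 0.05 in a two-tailed (non-directional) test", "as our primary outcome is the pain index score". AUA is therefore not the primary outcome, and no power or sample size is stated for it.

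**The concern.** A symptom score measured before and after an intervention usually carries information from the first measurement to the second. The Introduction puts urinary urgency and frequency first among stent symptoms. The entry criteria set no limit on existing urinary symptoms, apart from excluding patients already taking a genitourinary anticholinergic. No stratification by baseline symptoms is described. Patients may therefore differ in AUA score before any stent is placed. If the analysis ignores that, the variation stays in the error term.

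Two things are at stake. One is precision: a real difference in urinary symptoms between the stents could be missed when data already in hand would have shown it. The other is prespecification. Follow-up score, change score and adjusted score are three different analyses with different precision, and the plan leaves the choice open until the data have been seen.

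**Working it through.** **Inputs from the documents**
- Sample size: the trial "will enroll 100 participants" (Study design), with a possible 100 more after the interim analysis.
- Allocation: "Patients will be randomized in a 1:1 ratio for stent composition, soft vs. hydrophobic, for a total of 50 patients in each cohort" (Day 0), so n = 50 per arm.
- Alpha: two-sided 0.05 (Power Analyses). It is stated for the pain score and borrowed here for AUA.

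**Inputs the documents do not give (assumptions)**
- True AUA difference: 0.5 SD.
- Correlation rho between baseline and follow-up AUA: 0.1 to 0.7.

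**The plan's own figures.** These concern the pain score only. The simulation count reproduces: 3 sample sizes × 3 SDs × 24 differences × 1000 = 216,000. The "standard deviation of the population" was set at 1, 3 and 5. At 50 per arm, a difference of 3 and SD 5, noncentral-t power is 84.4%, which agrees with the plan's qualitative remark on power at 100 patients. There is no AUA figure to reproduce.

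**Unadjusted comparison of follow-up AUA.** The noncentrality is d × √(n/2) = 0.5 × √25 = 2.50 on 98 degrees of freedom. Power is 69.7%.

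**ANCOVA on baseline AUA.** The residual variance is multiplied by 1 − rho², so the noncentrality becomes 2.50/√(1 − rho²), with 97 degrees of freedom because one is spent on the covariate.

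| rho | 1 − rho² | Noncentrality | Power | Gain (points) |
|---|---|---|---|---|
| 0.1 | 0.99 | 2.51 | 70.1% | 0.4 |
| 0.2 | 0.96 | 2.55 | 71.4% | 1.7 |
| 0.3 | 0.91 | 2.62 | 73.7% | 4.0 |
| 0.4 | 0.84 | 2.73 | 77.1% | 7.4 |
| 0.5 | 0.75 | 2.89 | 81.5% | 11.8 |
| 0.6 | 0.64 | 3.13 | 87.2% | 17.5 |
| 0.7 | 0.51 | 3.50 | 93.4% | 23.7 |

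A simulation of 4000 trials per rho gave about 69% unadjusted, against 73%, 82% and 94% adjusted at rho 0.3, 0.5 and 0.7. This agrees with the table. At rho 0.5 the adjusted analysis of 100 patients is as precise as an unadjusted analysis of 100/0.75 ≈ 133.

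**Fewer evaluable patients.** With 45 per arm and rho 0.5, power goes from 65.0% to 77.3%.

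**Change score.** If the SD is equal at the two times, the variance of a change score is 2(1 − rho) times that of the follow-up score. The factor is 1.4 at rho 0.3, 1.0 at rho 0.5 and 0.6 at rho 0.7. Below rho 0.5 a change score is less precise than ignoring baseline. ANCOVA is at least as precise as either, apart from the one degree of freedom.

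**The case against.** A reader might infer that the plan has decided to discard baseline AUA and compare follow-up scores only. The documents do not support that. The plan is silent: a t-test or U-test can be run on change scores, and the multivariate methods it mentions could include ANCOVA. Nor does Covariate data say that nothing else may enter a model. What stands is that no use of baseline AUA is specified.

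A reader might also infer bias from chance baseline imbalance. Randomisation keeps the unadjusted comparison unbiased, and its standard error already allows for such imbalance. The issue is efficiency.

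The size of the gain is open to challenge, and that challenge stands. Low correlation cannot be ruled out. Baseline may be taken as much as 28 days ahead of surgery in patients with active stone disease, whereas the first follow-up score reflects a stent in place in patients discharged on tamsulosin. At rho 0.1 to 0.3 the gain is only 0.4 to 4.0 points. The documents set no power target for AUA, so no stated target is missed.

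Nor can baseline be assumed complete. Patients are asked to fill in the form, and Risks and Benefits lets them skip questions, so an adjusted analysis needs a rule for missing baseline scores.

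Finally, the same gap affects the primary pain score, where it matters more. That is a reason to fix both in one sentence; it does not supply a specification for AUA.

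**Conclusion.** The point holds as a prespecification and efficiency gap on a non-primary outcome. Baseline AUA is collected with no stated analytic use. The unadjusted comparison would be valid, but it may be less precise than the data permit.

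Under the assumptions of 50 per arm, a true difference of 0.5 SD and two-sided 0.05, the power gain is under 2 points at a correlation of 0.2, 4 points at 0.3, about 12 at 0.5 and about 24 at 0.7. It passes 5 points at a correlation of about 0.35. The documents cannot show where in this range the trial lies, so no single figure should be quoted as the loss. The recommendation does not depend on a high correlation, because at a low one ANCOVA costs essentially nothing.

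Baseline AUA could also serve as a covariate for urinary symptoms on USSQ 1 and 2, which have no baseline of their own. The documents do not show any benefit from this, so it is optional.

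**What to change.** 1. In Planned Statistical Analysis, state that AUA at stent removal and AUA at Day 7 will each be compared between arms by ANCOVA, with terms for randomised arm and baseline AUA, reporting the adjusted mean difference with its 95% confidence interval.
2. Add baseline AUA to Covariate data.
3. State a simple rule that keeps patients with a missing baseline score in the analysis, for example mean imputation of the baseline covariate.
4. Keep the unadjusted t-test or U-test as a sensitivity analysis.
5. Apply the same sentence to the primary pain score, with the baseline analog pain scale as covariate, and add that scale to Covariate data.
6. Optionally, use baseline AUA as a covariate for the urinary-symptom part of USSQ 1 and 2.

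The cost is wording and one degree of freedom per model. The forms are already scheduled, so no new visits, data or patients are needed. The text should be settled before outcome data are examined, and so before the interim analysis at 100 patients.
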